11.2.3 Causality

The investigator must determine the relationship between the administration of IP and the occurrence of an AE/SAE as Not Suspected or Suspected as defined below:

- Not suspected: Means a causal relationship of the adverse event to IP administration is **unlikely or remote**, or other medications, therapeutic interventions, or underlying conditions provide a sufficient explanation for the observed event.
- Suspected: Means there is a **reasonable possibility** that the administration of IP caused the adverse event. 'Reasonable possibility' means there is evidence to suggest a causal relationship between the IP and the adverse event.

Causality should be assessed and provided for every AE/SAE based on currently available information. Causality is to be reassessed and provided as additional information becomes available.

If an event is assessed as suspected of being related to a comparator, ancillary or additional IP that has not been manufactured or provided by Celgene, please provide the name of the manufacturer when reporting the event.

11.2.4 Duration

For both AEs and SAEs, the investigator will provide a record of the start and stop dates of the event.

11.2.5 Action Taken

The investigator will report the action taken with IP as a result of an AE or SAE, as applicable (e.g., discontinuation, interruption, or reduction of IP, as appropriate) and report if concomitant and/or additional treatments were given for the event.

11.2.6 Outcome

The Investigator will report the outcome of the event for both AEs and SAEs.

All SAEs that have not resolved upon discontinuation of the subject's participation in the study must be followed until recovered, recovered with sequelae, not recovered or death (due to the SAE).

11.3 Abnormal Laboratory Values

An abnormal laboratory value is considered to be an AE if the abnormality:

- results in discontinuation from the study;
- requires treatment, modification/ interruption of IP dose, or any other therapeutic intervention; or
- is judged to be of significant clinical importance, eg, one that indicates a new disease process and/or organ toxicity, or is an exacerbation or worsening of an existing condition.

Regardless of severity grade, only laboratory abnormalities that fulfill a seriousness criterion need to be documented as a serious adverse event.

If a laboratory abnormality is one component of a diagnosis or syndrome, then only the diagnosis or syndrome should be recorded on the AE page/screen of the CRF. If the abnormality was not a part of a diagnosis or syndrome, then the laboratory abnormality should be recorded as the AE. If possible, the laboratory abnormality should be recorded as a medical term and not simply as an abnormal laboratory result (e.g., record thrombocytopenia rather than decreased platelets).

11.4 Pregnancy

All pregnancies or suspected pregnancies occurring in either a female subject or partner of a male subject are immediately reportable events.

In the event of a pregnancy occurring in a female subject of childbearing potential or female partner of a male subject, Celgene will follow up with the clinical investigator each trimester of pregnancy and for 1 year following the birth of the infant (if applicable). Please reference the pregnancy information consent (permission) forms for data collection for additional information.

11.4.1 Females of Childbearing Potential

Pregnancies and suspected pregnancies (including elevated β human chorionic gonadotropin [β hCG] or a positive pregnancy test regardless of age or disease state) of a female subject occurring while the subject is on lenalidomide, or within 28 days of the subject's last dose of lenalidomide, are considered immediately reportable events. Lenalidomide is to be discontinued immediately and the subject instructed to return any unused portion of the IP to the investigator. The pregnancy, suspected pregnancy, or positive pregnancy test must be reported to Celgene Drug Safety immediately by facsimile, or other appropriate method, using the Pregnancy Initial Report Form, or approved equivalent form. The exposure of any pregnant female (e.g., caregiver or pharmacist) to lenalidomide, is also an immediately reportable event.

The female subject should be referred to an obstetrician-gynecologist, preferably one experienced in reproductive toxicity for further evaluation and counseling.

The Investigator will follow the female subject until completion of the pregnancy, and must notify Celgene Drug Safety immediately about the outcome of the pregnancy (either normal or abnormal outcome) using the Pregnancy Follow-up Report Form, or approved equivalent form.

If the outcome of the pregnancy was abnormal (e.g., spontaneous abortion), the investigator should report the abnormal outcome as an AE. If the abnormal outcome meets any of the seriousness criteria, it must be reported as an SAE to Celgene Drug Safety by facsimile, or other appropriate method, within 24 hours of the investigator's knowledge of the event using the SAE Report Form, or approved equivalent form.

All neonatal deaths that occur within 28 days of birth should be reported, without regard to causality, as SAEs. In addition, any infant death after 28 days that the investigator suspects is related to the in utero exposure to the IP should also be reported to Celgene Drug Safety by facsimile, or other appropriate method, within 24 hours of the investigator's knowledge of the event using the SAE Report Form, or approved equivalent form.

11.4.2 Male Subjects

If a female partner of a male subject taking investigational product becomes pregnant, the male subject taking IP should notify the investigator, and the pregnant female partner should be advised to call their healthcare provider immediately.

11.5 Reporting of Serious Adverse Events

Any AE that meets any criterion for an SAE requires the completion of an SAE Report Form in addition to being recorded on the AE page/screen of the CRF. All SAEs must be reported to Celgene Drug Safety within 24 hours of the investigator's knowledge of the event by facsimile, or other appropriate method, using the SAE Report Form, or approved equivalent form. This instruction pertains to initial SAE reports as well as any follow-up reports.

Second primary malignancies will be monitored as events of interest and must be reported as serious adverse events regardless of the treatment arm the subject is in (see Section 6.2.2). This includes any second primary malignancy, regardless of causal relationship to IP (study drug[s] or control), occurring at any time for the duration of the study, from the time of signing the ICD

for 5 years from the date the last subject initiates induction therapy. Events of second primary malignancy are to be reported using the SAE report form and must be considered an "Important Medical Event" if no other seriousness criteria apply; these events must also be documented in the appropriate page(s) of the CRF and subject's source documents. Documentation on the diagnosis of the second primary malignancy must be provided at the time of reporting as a serious adverse event (e.g., any confirmatory histology or cytology results, X-rays, CT scans, etc.).

The investigator is required to ensure that the data on these forms is accurate and consistent. This requirement applies to all SAEs (regardless of relationship to IP) that occur during the study (from the time the subject signs informed consent until 28 days after the last dose of IP), and any SPM occurring at any time during the study including follow-up period (if applicable) or any SAE made known to the investigator at anytime thereafter that are suspected of being related to IP. SAEs occurring prior to treatment (after signing the ICF) will be captured.

The SAE report should provide a detailed description of the SAE and include a concise summary of hospital records and other relevant documents. If a subject died and an autopsy has been performed, copies of the autopsy report and death certificate are to be sent to Celgene Drug Safety as soon as these become available. Any follow-up data should be detailed in a subsequent SAE Report Form, or approved equivalent form, and sent to Celgene Drug Safety.

Where required by local legislation, the investigator is responsible for informing the IRB/EC of the SAE and providing them with all relevant initial and follow-up information about the event. The investigator must keep copies of all SAE information on file including correspondence with Celgene and the IRB/EC.

11.5.1 Safety Queries

Queries pertaining to SAEs will be communicated from Celgene Drug Safety to the site via facsimile or electronic mail. The response time is expected to be no more than five (5) business days. Urgent queries (e.g., missing causality assessment) may be handled by phone.

11.6 Expedited Reporting of Adverse Events

For the purpose of regulatory reporting, Celgene Drug Safety will determine the expectedness of events suspected of being related to lenalidomide based on the investigator Brochure.

In the United States, all suspected unexpected serious adverse reactions (SUSARs) will be reported in an expedited manner in accordance with 21 CFR 312.32.

Celgene or its authorized representative shall notify the investigator of the following information:

- Any AE suspected of being related to the use of IP in this study or in other studies that is both serious and unexpected (ie, SUSAR).
- Any finding from tests in laboratory animals that suggests a significant risk for human subjects including reports of mutagenicity, teratogenicity, or carcinogenicity.

Where required by local legislation, the investigator shall notify his/her IRB/EC promptly of these new serious and unexpected AE(s) or significant risks to subjects.

The investigator must keep copies of all pertinent safety information on file including correspondence with Celgene and the IRB/EC (See Section 15.3 for record retention information).

Celgene Drug Safety Contact Information:

For Celgene Drug Safety contact information, please refer to the Serious Adverse Event Report Form Completion Guidelines or to the Pregnancy Report Form Completion Guidelines.

12 DISCONTINUATIONS

12.1 Treatment Discontinuation

The following events are considered sufficient reasons for discontinuing a subject from the investigational product:

- Adverse event(s)
- PD or relapse
- Subject withdrawal (subject no longer wants to receive study drug, but is willing to have additional data collected)
- Withdrawal of consent (both from treatment and study, including release of further subject data)
- Death
- Lost to follow-up
- Protocol violation
- Lack of efficacy
- The completion of study treatment (the completion of 30 Cycles for subjects in arm B) as per protocol

The reason for discontinuation should be recorded in the CRF and in the source documents.

12.2 Study Discontinuation and Completion

The following events are considered sufficient reasons for discontinuing a subject from follow-up in the study:

- Screen failure
- Withdrawal of consent (including release of further subject data).
- Death
- Lost to follow-up
- Protocol violation
- Lack of efficacy

The reason for discontinuation should be recorded in the CRF and in the source documents.

Once the 114 PFS events are confirmed, the follow-up period will continue for 5 years after the last subject has initiated induction therapy, and all subjects who are in the follow-up period will be deemed as completed and will be off boarded from the study

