Subjects may discontinue treatment earlier than described if they experience relapse or disease progression, unacceptable toxicity, or withdrawal of consent. All subjects who discontinue treatment or complete treatment will be followed for disease progression, subsequent anti-lymphoma therapy, and second primary malignancies (SPMs) for 5 years after the last subject has initiated induction therapy. Upon confirming 114 PFS events, all subjects who discontinue treatment or complete treatment will be followed for SPMs and overall survival for 5 years after the last subject has initiated induction therapy.

Assessments during the Screening, Treatment and Follow-up period are described in Table 1.

Efficacy determination for the primary endpoint will be based upon progression-free survival (PFS). See Section 10 for a description of the Statistical Analyses.

An independent external Data Monitoring Committee (DMC) will review safety data in an ongoing, periodic manner throughout the study. The frequency of DMC meetings will be documented in the DMC Charter.

The study will be conducted in compliance with Good Clinical Practices (GCPs).

Study Population

Subjects must have an investigator-assessed diagnosis of relapsed/refractory follicular lymphoma (FL) Grades 1, 2, 3a, or 3b(Gr 1-3b), transformed follicular lymphoma (tFL), marginal zone lymphoma (MZL), or mantle cell lymphoma (MCL), Stages I to IV, have been previously treated for their lymphoma with at least one prior line of therapy, have at least one measurable nodal or extranodal lesion by computed axial tomography (CT) or magnetic resonance imaging (MRI) scan, and have adequate bone marrow function, liver function, and renal function.

Length of Study

The expected accrual duration for 500 subjects is approximately 63 months. Subjects will receive protocol-specified treatment until relapse or progression of disease, withdrawal of consent or unacceptable toxicity. The study duration to events for primary analysis is estimated to be 105 months. The duration of the entire study will be approximately 10 years (accrual period of approximately 5 years plus 5 years from last subject initiating induction therapy).

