4.1.4 Randomization to Maintenance Treatment Period

After 12 cycles of lenalidomide plus rituximab induction therapy, subjects achieving CR/CRu, PR or having SD will be randomized to enter the maintenance period. During the maintenance period, subjects randomized to Arm B will receive rituximab (only) administered for 18 Cycles. Subjects randomized to Arm A will receive lenalidomide plus rituximab treatment for 18 Cycles and then lenalidomide until relapse or progression of disease. Lenalidomide (only) treatment in Arm A will be given per subject and/or physician discretion as described in detail in Section 8 and must begin no later than 1 week after the last cycle of rituximab plus lenalidomide. Subjects randomized under previous protocol (version 16 January 2014) who achieve a response of SD or better at the end of the Induction Treatment Period will remain in their originally assigned arm of maintenance therapy.

All subjects (in both Induction and Maintenance Treatment Periods) receive treatment as described unless they withdraw consent from treatment, experience unacceptable toxicities or have disease progression. Once subjects discontinue or complete treatment, they enter the follow-up period. All enrolled subjects will be followed for disease progression using the schedule described in Table 1. Subjects who progress before the end of planned treatment will enter the Follow-up Period. Determination of disease progression will be based on investigator assessment. All subjects who discontinue the protocol-specified treatment early for any reason without documented evidence of disease progression will also be followed in the Follow-up Period.

All subjects who will be on treatment upon reaching 5 years after the last subject has initiated induction therapy will continue the treatment and will be followed up for safety purposes only.

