4.1.5 Follow-up Period

Upon completion or discontinuation of the protocol-specified treatment, subjects will enter the Follow-up Period. In the Follow-up Period, all subjects will be followed for survival, time to next lymphoma treatment, and SPMs for 5 years after the last subject has initiated induction therapy unless they withdraw consent from the study, die or are lost to follow-up. Subjects whose disease has not yet progressed will also be followed for disease progression.

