^b All enrolled subjects are followed for disease progression using the same schedule described in Table 1. This includes subjects who discontinue the protocol-specified treatment or the study early for any reason without documented evidence of PD or relapse.

^c Upon confirmation of 114 PFS events, subjects will be followed up for survival and SPM as detailed in the follow-up section. See Section 4.1.6.

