6.2 Safety Assessments

Serial assessments of safety will be performed as outlined in the Schedule of Study Assessments (Table 1).

Time to histological transformation will be measured based on documentation of histological transformation as assessed by the investigator. The date of the histology/pathology report will be used as the date of transformation. In case of clinical suspicion of transformation, including rapid disease progression, unexpected changes in "B" symptoms or rapidly increasing lactate dehydrogenase (LDH), a biopsy should be performed. In this clinical trial, histological transformation will be considered disease progression.

Subjects who relapse or progress will continue to be followed for SPMs for 5 years from the date of the last subject initiates induction therapy.

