6.3 Efficacy Assessments

Radiological assessments for efficacy will be CT scan or MRI, to confirm the presence of measurable disease of > 1.5 cm in the transverse diameter at baseline. A CT is to be performed with contrast unless it is medically contraindicated. The regions to be imaged can be the neck, chest, and abdomen/pelvis, as well as any other regions clinically indicated for tumor imaging. The same imaging modality and regions for lesion evaluation at Screening must be consistently used throughout the study. CT/MRI scan performed for the purpose of standard of care may be used as the Screening CT scan if it is obtained within 8 weeks prior to C1D1.

All CT or MRI scan assessments will be determined from first dose date and will follow the counting of the dosing Cycles (ie, 1 cycle = 28 days). It is critical that the same modality used at Screening be used throughout the study for each subject. The scans must be performed:

- At 3 cycles after C1D1 (84 days \pm 2 weeks)
- At 6 cycles after C1D1 (168 days \pm 2 weeks)
- then every 6 cycles (168 days \pm 2 weeks) for 5 years
- and annually (± 3 weeks) thereafter until disease progression, relapse, or initiation of new antilymphoma therapy
- After the confirmation of the 114 PFS events, no efficacy assessments will be conducted

A subject with positive bone marrow at Screening will have a repeat bone marrow biopsy to confirm radiological CR only if the subject has otherwise fulfilled the criteria for a nodal CR; this bone marrow biopsy should be performed within 28 days after the criteria for CR have otherwise been met.

In addition to CT/MRI scan to assess disease, subjects with MZL involving the gastric area will undergo endoscopy as part of the response assessment. Subjects will have a repeat gastric biopsy for histological evaluation if the subject has fulfilled the IWG criteria for response of at least a CR/CRu. Histological evaluation will be performed by local pathologies laboratories using the GELA grading system (Copie-Bergman, 2003; Copie-Bergman, 2012; see also Section 6.1.6).

All enrolled subjects are followed for PD or relapse using the schedule described in Table 1.This includes subjects who discontinue treatment for any reason without documented evidence of PD or relapse. Subjects who start a new anti-lymphoma therapy without evidence of PD or relapse will not be followed by radiological assessments.

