Since the study endpoint is PFS based on CT, progression will typically be based on CT scans. In limited instances where progression is evident only by assessments other than CT, CT scans must still be provided along with the non-CT documentation of progression.

The radiological assessments (CT or MRI) and other assessments will be made according to a modification of the IWG 1999 criteria (Cheson, 1999), which are considered the primary method of response assessment. Scan results will be assessed by the Investigator or qualified site personnel. The modifications to the Cheson 1999 criteria are:

- Allow the inclusion of extranodal disease as measurable disease, as long as they fulfill all other requirements of measurable disease, including >1.5 cm in the longest transverse diameter.
- >2.0 cm bone marrow biopsy length is not required if the biopsy sample is considered adequate for assessment by the investigator.
- Gastric MALT subjects are required to undergo an additional evaluation of endoscopy and gastric biopsy at 2 time points within 3 months of radiologic evaluation demonstrating CR/CRu.
- PET scan is not considered part of the response criteria.

A similar modification to include extranodal disease as a measurable disease has been used previously (Fisher, 2006; Kane, 2007). The additional assessments – clinical assessments, bone marrow biopsy assessments, and endoscopic assessments (including biopsy) – are considered confirmatory to the initial CT scan findings. Bone marrow assessments are considered in the response assessment only in subjects with bone marrow involvement in the baseline bone marrow biopsy. Endoscopic biopsy and evaluation of the biopsy findings are required for confirmation of response only in subjects with an investigator-assessed pathologic diagnosis of MZL involving the gastric area. In those subjects whose CT/MRI response assessments require consideration of biopsy findings before a final response assessment can be determined, the date of achievement of a response status will be the initial date of CT or MRI showing a response.

Subjects who relapse or progress will continue to be followed for TTNLT and survival for 5 years from the date of the last subject initiating induction therapy.

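### Section 12.2 lets lack of efficacy or a protocol violation end study follow-up, contradicting Section 4.1.5 and Figure 1 footnote b, which keep such subjects in follow-up

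*Combined protocol and SAP*

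**What the plan says.** Section 12 separates leaving treatment (12.1) from leaving follow-up (12.2). Section 12.2 begins: "The following events are considered sufficient reasons for discontinuing a subject from follow-up in the study". Its six reasons are screen failure, consent withdrawal, death, loss to follow-up, protocol violation and lack of efficacy.

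Other current text sets a narrower exit rule or requires follow-up to continue:

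- Section 4.1.5 follows all subjects who have completed or stopped treatment for survival, next lymphoma treatment and SPMs, "unless they withdraw consent from the study, die or are lost to follow-up". Subjects who have not progressed are also followed for progression.
- Footnote b to Figure 1 (end of Section 4.2) applies the Table 1 progression schedule to all enrolled subjects: "This includes subjects who discontinue the protocol-specified treatment or the study early for any reason without documented evidence of PD or relapse".
- Section 6.3, after progression: "Subjects who relapse or progress will continue to be followed for TTNLT and survival for 5 years", counted from the last subject's start of induction.
- Section 6.2, after progression: "Subjects who relapse or progress will continue to be followed for SPMs for 5 years", counted the same way.

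Three further places concern subjects who stop treatment. The Protocol Summary says "All subjects who discontinue treatment or complete treatment will be followed for disease progression". Section 4.1.4 says that subjects who stop treatment early "for any reason without documented evidence of disease progression will also be followed in the Follow-up Period". Section 6.3 says of progression follow-up: "This includes subjects who discontinue treatment for any reason without documented evidence of PD or relapse".

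For PFS, Section 10.6.1 censors a subject without progression or death before the cut-off at the last visit with an adequate response assessment. It has no separate rule for subjects removed under Section 12.2.

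**The concern.** A site that reads Section 12.2 may close a subject's follow-up for lack of efficacy or a protocol violation. A site that reads Section 4.1.5 may not. The protocol states no order of precedence, and no blacked-out text accounts for the difference.

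Two kinds of data are at stake. After progression, the PFS event is already recorded, but OS, TTNLT and SPM data would stop. Before progression, PFS itself could be affected. A subject judged to be failing treatment may be close to progression, so ending observation there may be related to the outcome. Treatment is open label and progression is determined by the investigator, so the reason could be used differently in the two arms.

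**Working it through.** No arithmetic applies. The plan gives no figure for this point, and the documents give no count of removals. The check sets the texts side by side.

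**1. Is Section 12.2 really about follow-up?** Yes. Section 12.1 covers stopping investigational product and already contains both disputed reasons. Section 12.2 names follow-up in the study as its subject, so it cannot be read as a second treatment-stopping list.

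**2. Which texts conflict directly?**

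| Place | Who and what | Relation to 12.2 |
|---|---|---|
| 4.1.5 | All subjects off treatment; three exits only | Direct: neither disputed reason is an exit |
| Figure 1 footnote b | Progression follow-up, including subjects who left the study early without documented progression | Direct |
| 6.3, after progression | TTNLT and survival | Conflicts for a subject removed after progression |
| 6.2, after progression | SPMs | Conflicts for a subject removed after progression |
| Protocol Summary; 4.1.4; 6.3 on stopping treatment | Subjects who stop or complete treatment | Indirect: the scope is treatment, but the intent is continued follow-up |

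Footnote b is assigned to Figure 1 by its position, because the figure is not shown.

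**3. What follows if Section 12.2 is applied after progression?** The PFS event stands. OS would be censored at last contact and TTNLT at the last visit (Section 10.6.2). SPM reporting would end before the limit set in Section 6.2.2, which is five years after the last subject starts induction.

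**4. What follows if it is applied before documented progression?** The PFS effect needs every one of these conditions:

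- the subject was randomized and dosed in maintenance (the ITT definition in Section 10.2), so a removal during induction never enters the PFS analysis;
- no progression is on record;
- no new anticancer therapy has started, since Section 10.6.1 censors that subject at the last scan beforehand whatever Section 12.2 says;
- the later progression or death is not captured after removal.

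Such a subject is censored under Section 10.6.1 at the last adequate assessment.

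**5. Can lack of efficacy be used without progression?** Section 12.1 lists progression or relapse separately from lack of efficacy, which suggests that the two differ. Section 12.2 has no progression item, so there the term might mean progression. It is not defined in either section.

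**6. Does the event target change this?** The final analysis is triggered by 114 PFS events. Removals would not by themselves lower that number. They could delay reaching it and could make the censoring informative.

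**The case against.** The best defence is that Section 12.2 is a generic disposition list. It includes screen failure, which cannot apply to a subject in follow-up. It permits removal and does not require it. The rest of the protocol points consistently the other way, so a careful site would keep following the subject. Because Section 12.2 has no progression item, lack of efficacy may simply mean progression there, in which case PFS is untouched.

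Much of this stands. It narrows the consequence, and it makes the PFS effect depend on how an undefined term is used. It does not remove the contradiction. Section 12.2 tells sites to record the reason in the CRF, so the list is in operational use. Even if lack of efficacy means progression, removal still stops the survival, TTNLT and SPM follow-up required after progression.

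The disposition summary in Section 10.5 might be said to reveal the problem. It covers reasons for study discontinuation in all enrolled subjects, but does not mention arm, progression status or new therapy. Section 4.4 refers to a Statistical Analysis Plan, which may specify more; the text available does not.

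A reader might infer that the primary PFS comparison is biased, or attach a change in hazard ratio, power or type I error to this point. The documents do not support that. They show no removed subject, and any such figure would need an assumed number of removals, an assumed split between arms and assumed timing close to an event. If the same share of events were lost in both arms, the hazard ratio would be essentially unchanged.

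**Conclusion.** The contradiction is established in current text: Section 12.2 allows two exits from follow-up that Section 4.1.5 excludes and that footnote b overrides for non-progressed subjects. It should be corrected.

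Loss of OS, TTNLT and SPM data follows directly if Section 12.2 is applied after progression. An effect on PFS is only possible: it requires that lack of efficacy, or a protocol violation, be used before documented progression, and that all the conditions in step 4 hold. It would be wrong to read the point as saying that every subject removed under Section 12.2 is censored for PFS.

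The number of subjects affected, and the size and direction of any bias, cannot be determined from the documents. The recommendation rests on the conflict between the texts and the low cost of removing it.

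**What to change.** - Delete lack of efficacy and protocol violation from the Section 12.2 list. Leave Section 12.1 unchanged, since stopping treatment is a separate matter and is not in conflict.
- Add one sentence to Section 12.2 saying that subjects to whom these reasons apply remain in follow-up under Sections 4.1.5 and 6.3.
- For any subject already removed for either reason without withdrawing consent, resume whatever the protocol still requires at that time. Until 114 PFS events are confirmed, that is progression follow-up (if there has been no progression and no new anti-lymphoma therapy) and TTNLT. Survival and SPM follow-up continue throughout the period the protocol sets.
- Report by arm how many subjects were removed for each of the two reasons, with progression and new-therapy status at removal. This shows whether PFS could have been affected at all.

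No extra analysis that counts removals as PFS events is needed; Section 10.6.1 defines an event as objective progression or death.

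The cost is a protocol amendment, with IRB/EC approval unless it counts as administrative (Section 14.5), an extension of the disposition summary, and some site work to re-contact any removed subjects. No visit is added beyond those the protocol already requires.
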